### **8.3.4 Additional Analyses of the Primary Efficacy Endpoint(s)**

There are no additional analyses of the primary efficacy endpoint planned for this study.

## **8.4 Secondary Efficacy Analyses**

### **8.4.1 Key Secondary Efficacy Analyses**

The following ranked key secondary endpoints will be tested between each risankizumab dose group and the placebo group with a graphical multiple testing procedure as described in Section 12.0.

1. the proportion of subjects achieving validated Investigator Global Assessment Scale for Atopic Dermatitis (vIGA-AD) of "0" or "1" (on a 5-point scale) with a reduction from Baseline of  $\geq 2$  points at Week 16.
2. the proportion of subjects achieving a reduction of  $\geq 4$  points in worst pruritus NRS from Baseline to Week 16.

The corresponding null hypotheses for the ranked secondary endpoints are:

1. There is no difference between each of the risankizumab dose group (150 mg and 300 mg, respectively) and placebo group in the proportion of subjects achieving vIGA-AD of "0" or "1" (on a 5-point scale) with a reduction from Baseline of  $\geq 2$  points at Week 16.
2. There is no difference between each of the risankizumab dose group (150 mg and 300 mg, respectively) and placebo group in the proportion of subjects achieving a reduction of  $\geq 4$  points in worst pruritus NRS from Baseline to Week 16.

### **8.4.2 Other Secondary Efficacy Analyses**

All other secondary efficacy endpoints as listed in Section 3.3 will be evaluated by treatment group at each specified time point.

For each of the key efficacy endpoints as well as each of the other binary secondary efficacy endpoints, pairwise comparison of each risankizumab group versus placebo group will be analyzed using NRI method. All other continuous secondary endpoints will be analyzed using MMRM method.

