### 2.3 Treatment Assignment and Blinding

Each subject will be assigned a unique identification number by the IRT at the screening visit. Subjects who rescreen will use the same unique identification number from the initial screening visit. In addition, the IRT will assign a unique randomization number that will encode each subject's treatment group assignment according to the randomization schedule generated by the statistics department at AbbVie.

At the Baseline visit, subjects meeting eligibility criteria will be randomized in a 2:2:1 ratio to risankizumab 150 mg, risankizumab 300 mg, or matching placebo.

Randomization at Baseline will be stratified by baseline disease severity (moderate [vIGA-AD 3] vs. severe [vIGA-AD 4]) and geographic region (Japan vs. Rest of the World [RoW]).

At the Week 16 visit, subjects receiving placebo in Period A will be re-randomized in a 1:1 Ratio to receive either risankizumab 150 mg or risankizumab 300 mg through Week 52. Subjects originally randomized to risankizumab 150 mg or 300 mg in Period A will stay on their previously assigned treatment through Week 52. There is no stratification at the re-randomization at Week 16.

To maintain the blind, all risankizumab and placebo kits provided for the study will be identical in appearance. AbbVie personnel will remain blinded until the primary analysis at Week 16 is available. The study sites and subjects will remain blinded to treatment assignments for the entire duration of the study.

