## **2.4 Sample Size Determination**

Approximately 155 subjects will be randomized to risankizumab 150 mg, risankizumab 300 mg, or placebo in a ratio of 2:2:1 (62 subjects each for the risankizumab 150 mg and 300 mg groups and 31 subjects for the placebo group). Assuming an EASI 75 response rate of at most 15% in the placebo group, this sample size will provide more than 90% power to detect the treatment difference of at least 36% between each risankizumab group and placebo group using a two-sided test at a 0.025 significance level.

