### **3.2 Secondary Endpoint(s)**

The key secondary endpoints for this study are:

1. The proportion of subjects achieving validated Investigator Global Assessment Scale for Atopic Dermatitis (vIGA-AD) of "0" or "1" (on a 5-point scale) with a reduction from Baseline of  $\geq 2$  points at Week 16.
2. The proportion of subjects achieving a reduction of  $\geq 4$  points in worst pruritus numerical rating scale (NRS) from Baseline to Week 16.

Other secondary endpoints that are not included in the multiplicity testing procedure (see Section 12.0) are listed below and will be evaluated for each of the specified time points:

- Percent change in EASI from Baseline to Week 16, Week 28, and Week 52.
- Proportion of subjects achieving EASI 75 at Week 28 and Week 52.
- Proportion of subjects achieving EASI 50 at Week 16, Week 28, and Week 52.
- Proportion of subjects achieving EASI 90 at Week 16, Week 28, and Week 52.
- Proportion of subjects achieving vIGA-AD of "0" or "1" with a reduction from Baseline of  $\geq 2$  points at Week 28 and Week 52.
- Change in body surface area (BSA) from Baseline to Week 16, Week 28, and Week 52.
- Proportion of subjects achieving 50% improvement in SCORing Atopic Dermatitis (SCORAD 50) at Week 16, Week 28, and Week 52.
- Proportion of subjects achieving SCORAD 75 at Week 16, Week 28, and Week 52.
- Proportion of subjects achieving SCORAD 90 at Week 16, Week 28, and Week 52.
- Proportion of subjects achieving Dermatology Life Quality index (DLQI) of "0" or "1" at Week 16, Week 28, and Week 52.
- Proportion of subjects achieving Children's Dermatology Life Quality index (CDLQI) of "0" or "1" at Week 16, Week 28, and Week 52.
- Proportion of subjects achieving a DLQI improvement of  $\geq 4$  points at Week 16, Week 28, and Week 52 among subjects with a DLQI  $\geq 4$  at Baseline.
- Change in DLQI from Baseline to Week 16, Week 28, and Week 52.
- Change in CDLQI from Baseline to Week 16, Week 28, and Week 52.

- Change in worst pruritus NRS from Baseline to Week 16, Week 28, and Week 52.
- Proportion of subjects achieving a reduction of  $\geq 4$  points in worst pruritus NRS from Baseline to Week 28 and Week 52.

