## 4.0 Analysis Populations

The following population sets will be used for the analyses.

The intent-to-treat (ITT) population, which includes all randomized subjects, will be used for all efficacy analyses. Subjects will be included in the analysis according to the treatment groups that they are randomized to. Subjects who are randomized to placebo in Treatment Period A and do not continue into Treatment Period B will be excluded from the analysis in Treatment Period B.

The following populations will be used for safety analyses:

- The safety population in Period A is defined as all subjects who are randomized at Baseline and received at least one dose of study drug in Treatment Period A. Subjects are assigned to a treatment group based on the treatment actually received.
- The safety population in Period B is defined as all subjects who received at least one dose of study drug in Treatment Period B. Subjects are assigned to a treatment group based on the treatment actually received.
- An All Risankizumab Treated Population (ALL\_RZB) will consist of all subjects who received at least one dose of risankizumab in the study. This population will be used to provide a comprehensive summary of safety.

For the safety populations, subjects are assigned to a treatment group based on the "as treated" treatment group, regardless of the treatment randomized. The "as treated" is determined by the first dose subject will receive for Period A, and is determined by the first dose subject will receive for Period B.

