## 9.4 Analysis of Vital Signs

Each vital sign variable will be summarized for all applicable time points (starting with Baseline) with the number of non-missing observations, mean and standard deviation, median, minimum and maximum. Mean change from baseline to each applicable post-baseline visit will be summarized for each vital sign variable, with the number of

observations, baseline mean, and visit mean. The change from baseline mean, standard error, and 95% confidence interval will be presented for the mean change from baseline within each treatment group and difference between treatment groups (risankizumab vs. placebo).

If applicable, summary statistics will also be provided for change from baseline height and weight at each scheduled visit for the adolescent group.

Vital sign variables will be evaluated based on potentially clinically significant (PCS) criteria ([Appendix C](#)). For each vital sign PCS criterion, the number and percentage of subjects who have a vital sign value meeting the criteria will be summarized. Listings will be provided to summarize subject-level vital sign data for subjects meeting PCS criteria.

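### SAP 8.1 and 8.4.2 let the placebo comparison run to Weeks 28 and 52, when no one is assigned placebo, in conflict with 8.2; Period B groups are pooled for safety and undefined for efficacy

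*SAP*

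**What the plan says.** - **Design.** SAP 2.3 says that at Week 16 "subjects receiving placebo in Period A will be re-randomized in a 1:1 Ratio to receive either risankizumab 150 mg or risankizumab 300 mg". The other two arms stay on their dose. The protocol synopsis confirms that all subjects are to receive risankizumab at Weeks 16, 28 and 40.
- **Endpoints.** SAP 3.2 lists, among the other secondary endpoints, "Proportion of subjects achieving EASI 75 at Week 28 and Week 52". The vIGA-AD 0/1 response and the NRS reduction of at least 4 points also appear in that list only at Weeks 28 and 52, because their Week 16 versions are key secondary. SAP 3.3 adds that primary and secondary variables are analysed at all visits.
- **Comparison rule.** SAP 8.4.2 says that for each of the other binary secondary endpoints "pairwise comparison of each risankizumab group versus placebo group will be analyzed using NRI method", and it gives the continuous ones to MMRM. SAP 8.1 states the placebo contrast for categorical and continuous variables in general. None of these sentences names a period.
- **Period rule.** SAP 8.2 makes NRI-C and MMRM the primary approaches in Period A and uses observed cases (OC) for long-term efficacy summaries of all variables in Period B. The version history records the OC rule as a clarification made in version 5.0.
- **Grouping.** Efficacy is analysed as randomised (SAP 4.0). For safety in Period B, the treatment group "is determined by the first dose subject will receive for Period B", and 9.1 repeats this. No placebo-to-risankizumab group is named anywhere.

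**The concern.** After the Week 16 switch there are four treatment sequences: 150/150, 300/300, placebo/150 and placebo/300. The SAP's analysis rules do not recognise them.

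On efficacy, a programmer who follows 8.4.2 would produce a Week 28 or Week 52 table with a column labelled placebo made up of subjects assigned risankizumab. A difference that shrinks as those subjects catch up could then be read as the drug losing effect. A programmer who follows 8.2 would produce an OC summary with no contrast. The sponsor is unblinded at the Week 16 analysis, so if the conflict is left open, someone who can see the allocation may have to choose between the two readings.

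On safety, pooling by first Period B dose mixes subjects meeting the drug for the first time with subjects receiving their third dose. The Operations Manual (3.11) gives the Week 16 injection the same two-hour hypersensitivity watch as Baseline, yet the Period B tables would not separate the two kinds of subject.

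**Working it through.** **1. The plan's own figure.** SAP 2.4 gives 62, 62 and 31 subjects and a two-sided level of 0.025. "Assuming an EASI 75 response rate of at most 15% in the placebo group", it claims "more than 90% power to detect the treatment difference of at least 36% between each risankizumab group and placebo group". With 15% versus 51% and 31 versus 62 subjects:

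- pooled rate = (31 × 0.15 + 62 × 0.51)/93 = 0.39
- SE under the null = √(0.39 × 0.61 × (1/31 + 1/62)) = 0.1073
- SE under the alternative = √(0.15 × 0.85/31 + 0.51 × 0.49/62) = 0.0902
- power = Φ((0.36 − 2.241 × 0.1073)/0.0902) = 90.7%

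The stated power reproduces. It is a Week 16 figure, and nothing below changes it.

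**2. Do the sections conflict?** Yes.

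- EASI 75, vIGA-AD 0/1 and the NRS response, as listed in 3.2, have no Week 16 version for 8.4.2 to act on. Their only listed time points fall when no subject is assigned placebo.
- 8.2 points the other way, with OC summaries for Period B. But its closing paragraph says that, in both periods, subjects are non-responders under NRI and missing under OC and MMRM after rescue or prohibited medication. Permitted rescue starts only after the Week 24 assessments (Protocol 5.4). So 8.2 itself leaves NRI and MMRM in play for Period B.

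**3. What the literal contrast measures.** Scheduled doses come from Operations Manual 6.1: Weeks 0, 4, 16, 28 and 40 for continuing subjects, and Weeks 16, 28 and 40 for switchers.

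| Assessment | Continuing: prior doses | Switchers: prior doses | Switchers: weeks since first risankizumab dose |
|---|---|---|---|
| Week 28, before injection | 3 | 1 | 12 |
| Week 52 | 5 | 3 | 36 |

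The documents give no Period B response rates. Assume continuing subjects stay at the design rate of 51% and let the originally-placebo subjects vary:

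| Assumed rate, originally placebo | Apparent difference from placebo |
|---|---|
| 15% | 51 − 15 = 36 points |
| 33% | 51 − 33 = 18 points |
| 51% | 51 − 51 = 0 points |

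The drug's effect is held constant throughout, so the contrast reflects only how far switchers have caught up.

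**4. Composition of the Period B safety groups.** Switchers per dose = 31/2 = 15.5. Group size = 62 + 15.5 = 77.5. Switcher share = 15.5/77.5 = 20%. If 10% or 20% of placebo subjects alone are lost before Week 16 (assumption), the share is 13.95/75.95 = 18.4% or 12.4/74.4 = 16.7%.

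**5. Period B efficacy groups.** SAP 4.0 drops only placebo subjects who do not enter Period B. Those who do enter stay in the analysis as randomised, under a label the SAP never defines for that period.

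**The case against.** The strongest reply is that 8.2 already settles the efficacy question: it defines the NRI method, makes NRI-C primary in Period A, and version 5.0 deliberately clarified that Period B is OC. This stands in part. A reader might infer from 8.4.2 that the sponsor has a settled plan to test against placebo at Weeks 28 and 52, and the documents do not support that. They support an unresolved conflict, because 8.4.2 was not aligned with 8.2 and 8.2 still describes NRI and MMRM handling in Period B.

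Other stronger readings are tempting and do not hold:

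- **Laboratory and vital signs.** SAP 9.3 and 9.4 ask at each applicable visit for the "difference between treatment groups (risankizumab vs. placebo" contrast, with no period limit. A reader might infer a placebo column at later visits. But safety groups follow the first dose received in each period (4.0, 9.1), and no one is assigned placebo in Period B, so that column is empty there.
- **Pooled efficacy.** One could compute a pooled EASI 75 rate of (62 × 0.51 + 15.5 × 0.15)/77.5 = 43.8% and call it dilution. First-dose grouping is specified for safety only, so the SAP does not order that analysis.
- **Unreadable safety.** An event confined to first exposure at 6% of switchers (assumed) would show as 6% × 15.5/77.5 = 1.2% in a pooled Period B group. That does not hide first-exposure safety. Period A shows it in 124 planned risankizumab subjects against 31 on placebo, and ALL_RZB counts events from each subject's first risankizumab dose, switchers included.
- **Everyone on drug.** This is true by assignment. Subjects who stop study drug remain in follow-up (Protocol 5.6).

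It is also fair to say that the pooled safety grouping is explicitly prespecified. It is a less informative choice, not an error of execution.

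**Conclusion.** The point holds in limited form. SAP 8.1 and 8.4.2 carry the risankizumab-versus-placebo comparison, without a Period A limit, to endpoints that exist only at Weeks 28 and 52, and this conflicts with 8.2. Taken literally, the result is an early-versus-delayed-start contrast under a placebo label. At an assumed 51% in continuing subjects and 15% to 51% in switchers, it could lie anywhere from 36 points to 0.

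Separately, each Period B safety dose group would be about 20% newly switched subjects (16.7% to 18.4% under the assumed placebo-only losses), and the Period B efficacy groups are undefined.

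The consequence is confined to Period B reporting. The Week 28 and 52 endpoints lie outside the multiplicity procedure (SAP 3.2), and the Week 16 primary and key secondary tests, their alpha and their power stand. It should be corrected because the correction costs little and the mislabelled table would be easy to misread.

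**What to change.** - **SAP 8.1, 8.4.2 and, for consistency, 8.5:** limit placebo comparisons and the NRI and MMRM methods to visits through Week 16, using assessments made before the Week 16 injection. State that Week 28 and 52 endpoints are summarised descriptively by OC, as in 8.2. Align the closing paragraph of 8.2 with this. While editing 8.4.2, correct its pointer: the secondary endpoints are in Section 3.2, not 3.3.
- **SAP 4.0 and 9.1:** define Period B groups by sequence (150/150, 300/300, placebo/150, placebo/300) and present Period B efficacy and safety by these groups, with no placebo contrast. Keep ALL_RZB as the pooled safety display.
- **SAP 9.3 and 9.4:** add Period A to the placebo difference. This is only a clarification.

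Make the change before the Week 16 unblinding. The cost is SAP wording and two extra table columns. The downside is that those columns hold about 15-16 subjects each, so one subject moves a percentage by 6 to 7 points (1/16 = 6.25%, 1/15 = 6.7%). They should be read descriptively.

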### **8.4.3 Supportive Secondary Efficacy Analyses**

There are no supportive secondary efficacy analyses planned for this study.

### **8.5 Additional Efficacy Analyses**

All variables listed in Section 3.5 are additional efficacy endpoints and will be evaluated at all applicable visits.

Categorical endpoints will be analyzed using NRI method. Continuous endpoints will be analyzed using MMRM method.

### **8.6 Efficacy Subgroup Analyses**

To evaluate the consistency of the efficacy over demographic and other baseline characteristics, the primary efficacy endpoint will be analyzed in the following subgroups:

- Age Group 1 (< 18 years, ≥ 18 - < 40 years, ≥ 40 – < 65 years, ≥ 65 years)
- Age Group 2 (< 18 years, ≥ 18 years)
- Sex (male, female)
- BMI (normal: < 25, over weight: ≥ 25 – < 30, obese: ≥ 30)
- Race (White, Asian, Black, and Other)
- Weight (< median, ≥ median)
- Geographic regions (Japan, rest of world)
- Baseline vIGA-AD (< 4, 4)
- Baseline EASI (< median, ≥ median)
- Intrinsic/non-allergic subtype (IgE level < 200 kU/L vs. IgE level ≥ 200 kU/L)
- Tobacco use (current; former/never/unknown)

- Treatment-emergent ADA status during Week 0 to Week 16 (yes vs. no)  
Treatment-emergent NAb status during Week 0 to Week 16 (yes vs. no)

A subgroup will be combined with the adjacent subgroup if there are less than 10% subjects in the subgroup. Any Race subgroup that contains less than 10% subjects will be combined with the Other Race subgroup for analyses.

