### **7.1 Demographics and Baseline Characteristics**

The following demographic and baseline characteristics will be summarized.

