### **Disease Characteristics**

- Continuous variables including the baseline assessment of the following:
  - EASI overall score and body region scores
  - vIGA-AD score
  - Worst pruritus Numerical Rating Scale (NRS)
  - Body Surface Area (BSA) in percentage
  - Scoring Atopic Dermatitis (SCORAD)
  - Dermatology Life Quality Index (DLQI)
  - Children's Dermatology Life Quality Index (CDLQI)
  - Patient Oriented Eczema Measure (POEM)
  - Patient Global Impression of Severity (PGIS)
  - Patient Global Impression of Change (PGIC)
  - EuroQoL Dimensions 5 Levels (EQ-5D-5L)
  - Atopic Dermatitis Symptom Scale (ADerm-SS) 7-item total symptom score (TSS-7)
  - ADerm-SS 11-item total symptom score (TSS-11)

- ADerm-SS skin pain score
- Atopic Dermatitis Impact Scale (ADerm-IS) domain scores (sleep, emotional state, daily activities)
- AD disease duration since diagnosis (years),
- AD disease duration since symptoms started (years),
- duration between symptoms and diagnosis of AD disease (years)
- Categorical variables including:
  - Baseline vIGA-AD score (< 4, 4)
  - Baseline vIGA-AD score (0, 1, 2, 3, 4)
  - Baseline EASI (< median, ≥ median)
  - Baseline Electrocardiogram (ECG) categories, including normal, abnormal – not clinically significant, abnormal – clinically significant, unable to evaluate, and details of the abnormality when applicable.
  - Intrinsic/non-allergic subtype (IgE level < 200 kU/L, IgE level ≥ 200 kU/L)
  - Treatment-emergent ADA status during Week 0 to Week 16 (yes, no)
  - Treatment-emergent NAb status during Week 0 to Week 16 (yes, no)
  - Tobacco user (current, former, never, unknown)
  - Alcohol user (current, former, never, unknown)

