#### **Analysis of Categorical Variables**

Categorical variables will be summarized by frequencies and percentage by each treatment group. Pairwise comparison of each risankizumab group versus placebo group will be performed using Cochran-Mantel-Haenszel (CMH) test, stratified by vIGA-AD categories (moderate [vIGA-AD 3] vs. severe [vIGA-AD 4]). Point estimates and 95% CIs for the difference in proportions between each risankizumab group and placebo will be provided. Construction of CIs for the common risk difference will be based on the Mantel-Haenszel estimate adjusting for the stratification factor.

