### **Analysis of Continuous Variables**

The model based mean and standard error will be provided for continuous variables. The Baseline and visit means will also be presented for each treatment group among subjects who have both Baseline and at least one post Baseline visit values. Treatment groups will be compared using MMRM model as described in Section 8.2 with treatment, vIGA-AD categories and the corresponding baseline value in the model. Point estimates and 95% CIs of mean change from baseline within treatment groups, and between each risankizumab treatment group and placebo will be provided.

Unless otherwise specified, any subject who is randomized based on a wrong stratum will be analyzed according to the actual stratum the subject belongs to.

"Baseline" refers to the last non-missing observation before the first administration of study drug or randomization if no study drug is given.

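### SAP 7.1 and 8.6 treat ADA and NAb status arising after first dose as baseline characteristics and EASI 75 subgroups, with essentially no placebo comparator among antibody-positive subjects

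*SAP*

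**What the plan says.** SAP 8.6 introduces its subgroup list this way: "To evaluate the consistency of the efficacy over demographic and other baseline characteristics, the primary efficacy endpoint will be analyzed in the following subgroups". Two of the rows that follow are "Treatment-emergent ADA status during Week 0 to Week 16 (yes vs. no" and "Treatment-emergent NAb status during Week 0 to Week 16 (yes vs. no".

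SAP 7.1 opens with "The following demographic and baseline characteristics will be summarized". Its Disease Characteristics list includes "Treatment-emergent ADA status during Week 0 to Week 16 (yes, no" and the same entry for NAb.

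SAP 8.1 defines Baseline as the last non-missing observation before the first dose, or before randomisation if no dose is given.

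On method, SAP 8.1 says of categorical variables: "Pairwise comparison of each risankizumab group versus placebo group will be performed using Cochran-Mantel-Haenszel (CMH) test", stratified by vIGA-AD category. SAP 8.3.3 repeats this for EASI 75. Section 8.6 names neither a test nor a comparator, and it makes no exception for the antibody rows. It does say that a subgroup holding under 10% of subjects is combined with the adjacent one.

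Protocol 7.5 plans ADA and nAb counts by dose group. It leaves the effect of ADA on efficacy as something that may be explored.

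**The concern.** A subgroup analysis of a randomised comparison keeps its protection only if the grouping variable was fixed before treatment. Antibody status that emerges over Weeks 0 to 16 is not fixed then. In this trial it is also a variable that one arm can hardly acquire, because the assay looks for antibodies to a drug that placebo subjects have not yet received.

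Run by the SAP's stated method, the antibody-positive level has almost no placebo side. The antibody-negative level compares a filtered risankizumab group with an essentially unfiltered placebo group. Both results would appear in the same display as true baseline subgroups such as age, sex and vIGA-AD. A reader could take the antibody-negative difference for a randomised effect, or conclude from it that the drug works better without ADA.

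**Working it through.** **1. Timing.** The definition of Baseline in SAP 8.1 ends at first dose; the two variables run from Week 0 to Week 16. They cannot meet the definition. This step needs no assumption.

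**2. Placebo exposure.** Protocol 5.7 gives placebo subjects only placebo syringes in Period A. Operations Manual 3.13 has ADA and nAb samples drawn within 60 minutes before dosing at dosing visits, so the Week 16 sample precedes a placebo subject's first risankizumab. The same section describes an assay for antibodies to risankizumab. Barring a dosing error, a positive placebo result is a false positive or cross-reactivity.

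**3. The plan's own figure.** SAP 2.4: 62 per dose versus 31 placebo, 51% (15% + 36%) versus 15%, two-sided 0.025, more than 90% power.
- Pooled rate = (62 × 0.51 + 31 × 0.15)/93 = 0.39.
- Null SE = √[0.39 × 0.61 × (1/31 + 1/62)] = 0.1073.
- Alternative SE = √[0.15 × 0.85/31 + 0.51 × 0.49/62] = 0.0902.
- Power = Φ[(0.36 − 2.241 × 0.1073)/0.0902] = Φ(1.32) = 90.7%.

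The stated power is reproduced, and nothing in this point changes it.

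**4. Antibody-positive level.** The documents give no ADA incidence, so a range is assumed.

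| Assumed incidence on risankizumab | Positive, of 124 | Per dose, of 62 | True placebo positives |
|---|---|---|---|
| 5% | about 6 | about 3 | 0 |
| 10% | about 12 | about 6 | 0 |
| 20% | about 25 | about 12 | 0 |
| 30% | about 37 | about 19 | 0 |

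With an assumed placebo false-positive rate of 1% to 5%, the expected placebo count is 31 × 0.01 = 0.3 to 31 × 0.05 = 1.6. The chance of none is 0.99^31 = 73% to 0.95^31 = 20%. With a single placebo positive, one of the two vIGA-AD strata would still lack a comparator.

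**5. Merge rule.** Taking the 10% over all 155 subjects, 0.10 × 155 = 15.5, so at least 16 positives are needed. If none is on placebo, that is 16/124 = 12.9% of risankizumab subjects. Below this, a yes/no factor collapses into the whole population and no subgroup remains. Under Operations Manual 3.13, nAb testing is only for confirmed ADA-positive samples. NAb positives therefore cannot outnumber ADA positives, and the NAb row is the likelier to merge.

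**6. Antibody-negative level.** Let p be the response rate on risankizumab, and aR and aN the ADA rates in responders and non-responders. Then

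P(response | ADA-negative) = p(1 − aR) / [p(1 − aR) + (1 − p)(1 − aN)].

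With p = 0.51 and essentially all placebo subjects at 15% (true difference 36 points):
- aR 10%, aN 20%: 0.459/(0.459 + 0.392) = 0.539, difference 38.9 points.
- aR 10%, aN 30%: 0.459/(0.459 + 0.343) = 0.572, difference 42.2 points.
- aR 20%, aN 10%: 0.408/(0.408 + 0.441) = 0.481, difference 33.1 points.
- aR = aN: 0.51, difference 36 points, no shift.

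Implied incidences in the first three cases are 14.9%, 19.8% and 15.1%, or about 18, 25 and 19 positives of 124. All pass the merge rule.

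With no drug effect (p = 0.15):
- aR 10%, aN 20%: 0.135/(0.135 + 0.680) = 0.166, a spurious 1.6 points.
- aR 10%, aN 30%: 0.135/(0.135 + 0.595) = 0.185, a spurious 3.5 points.

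**The case against.** **The comparator is not stated.** Section 8.6 says only that the endpoint will be analysed in the subgroups. A reader might infer that the SAP expressly orders a placebo comparison by antibody status; it does not. The inference rests on 8.1 and 8.3.3 being the only methods given and on 8.6 making no exception. It is the natural default. If a within-drug description was intended, the SAP should say so.

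**The merge rule may remove the problem.** This stands in part. At 5% or 10% incidence the ADA subgroup would not be run. At about 13% or more it would be, with the flaw intact.

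**The shift is assumed, small and of unknown direction.** This stands. A reader might infer that the antibody-negative result must favour risankizumab; the documents give neither an ADA incidence nor response by ADA status. The shift can be upward, downward or zero. It is also well inside sampling error: with about 53 versus 31 subjects at 53.9% and 15%, the unstratified 95% half-width is 1.96 × √(0.539 × 0.461/53 + 0.15 × 0.85/31), about 18 points.

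**The row labels show that the variables are post-baseline.** True, and the 7.1 entry has no inferential effect. The labels do not supply a placebo comparator in 8.6.

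**ADA and efficacy is a legitimate question, already foreseen in Protocol 7.5.** Agreed. That section foresees exploration, not a placebo-controlled subgroup. A within-dose table is still a non-randomised contrast. Its gain is honest labelling and the loss of an uninformative placebo column.

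**Conclusion.** Wrong as written. The baseline classification contradicts the SAP's own definition, and that part needs no assumption. Under the only categorical method the SAP provides, the antibody-positive difference from placebo is essentially inestimable, and the antibody-negative difference is not a randomised comparison. This applies once at least 16 of 155 subjects are positive; below that the merge rule leaves no subgroup.

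The size rests entirely on assumed ADA rates. A true 36-point difference reads as about 39 to 42 points if ADA occurs in 10% of responders and 20% to 30% of non-responders. It reads as about 33 if the rates are 20% and 10%, and is unchanged if ADA is unrelated to response.

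A reader might infer that the trial's main conclusion is at risk. It is not: the multiplicity procedure in SAP 12.0 covers only EASI 75, the vIGA-AD response and the pruritus response at Week 16. The primary analysis, sample size, power and alpha are unaffected.

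**What to change.** Remove the ADA and NAb rows from the baseline list in SAP 7.1 and from the subgroup list in SAP 8.6. Replace them with one descriptive table of EASI 75 at Week 16 by ADA and NAb status within each risankizumab dose group, with no placebo comparison, labelled post-baseline and non-randomised. A footnote should define treatment-emergent for these variables and say how subjects without a post-baseline sample are classed, since the SAP does neither.

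This fits the exploratory intent of Protocol 7.5. The cost is a wording change in two SAP sections and one table shell. It requires no new data and no change to sample size, alpha or the primary analysis.
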